### **Overview**

This section defines the types of safety data that will be collected under this protocol and outlines the procedures for appropriately collecting, grading, recording, and reporting those data. Adverse events that are classified as serious according to the definition of health authorities must be reported promptly (per Section 4, *Reporting of Serious Adverse Events and Adverse Events*) to the sponsor (OSCTI). Appropriate notifications will also be made to principal investigators, Institutional Review Boards (IRBs), and health authorities.

Information in this section complies with *ICH Guideline E2A: Clinical Safety Data Management: Definitions and Standards for Expedited Reporting*, *ICH Guideline E-6: Guideline for Good Clinical Practice*, 21CFR Parts 312 and 320, and applies the standards set forth in the National Cancer Institute (NCI), Common Terminology Criteria for Adverse Events (CTCAE), Version 4.0. <http://ctep.cancer.gov/reporting/ctc.html>.

### **Definitions, Grading, and Attribution of Adverse Events**

#### **Definitions**

##### **Adverse Event (AE)**

Any untoward or unfavorable medical occurrence associated with the subject's participation in the research, whether or not considered related to the subject's participation in the research (modified from the definition of adverse events in the 1996 International Conference on Harmonization E-6 Guidelines for Good Clinical Practice) (from OHRP "Guidance on Reviewing and Reporting Unanticipated Problems Involving Risks to Subjects or Others and Adverse Events (1/15/07)" at <http://www.hhs.gov/ohrp/policy/advevntguid.html>

For this study, an adverse event will include any untoward or unfavorable medical occurrence associated with:

- **Study therapy regimen.** Since the study processes involve only the 2-4 minutes between delivery and arrival to the neonatal resuscitation warmer, adverse events will be collected during this time period.

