We will aim for an operating room temperature of 65-70 degrees F. The surgical technician will be provided with the necessary neonatal wraps and mattresses in a sterile fashion, and they will ensure these are available on the surgical field once the cesarean has begun. In the intervention group, the thermal mattress will be activated immediately prior to hysterotomy and placed on the sterile field with delivery of the infant directly onto the mattress. The infant will be dried, stimulated and bulb suctioned as deemed necessary per standard of care followed by wrapping. In the non- intervention group, the infant will be delivered onto the sterile field, dried and suctioned as deemed necessary per OU standard. Cord clamping will be delayed for 60 seconds in all infants under the supervision of both the obstetrician and the neonatal resuscitation team. If either team believes delayed cord clamping is no longer considered safe, as is our usual protocol, the cord will be clamped and cut and the baby will be handed off to the neonatology team. After the infant is handed to the neonatology team along with all group assignment specific materials (wrap and thermal mattress, if in the intervention group), neonatal temperature will be assessed immediately upon arrival to the resuscitation warmer using a digital thermometer placed in the axillary space. Infant temperature will be recorded at 1) arrival to the warmer, 2) after the neonatologist deems that in-room resuscitation is complete and 3) at admission to the Neonatal Intensive Care Unit (NICU), Mother Baby Unit (MBU) or Post-Anesthesia Care Unit (PACU) depending on the baby's needs; determined by the resuscitating physicians. These measurements will be recorded by research nurses in a data collection sheet. Further, the research nurse will record the time from delivery to the time it takes for the infant to arrive at the warmer. Upon arrival at the warmer, the mattress and wrap will be removed as neonatal evaluation takes place.

As immediate neonatal temperature is not generally discussed with patients unless there is an issue such as concern for infection, neonatal temperature will not be routinely discussed with all participants. Only if there is concern for neonatal infection or if there is hyperthermia (>37.5 degrees C) will the study results be discussed with the patient.

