### Serious Adverse Event (SAE)

An adverse event or suspected adverse reaction is considered “serious” if, in the view of either the investigator or OSCTI, it results in any of the following outcomes (21 CFR 312.32(a)):

1. Death.
2. A life-threatening event: An AE or SAR is considered “life-threatening” if, in the view of either the investigator or OSCTI, its occurrence places the subject at immediate risk of death. It does not include an AE or SAR that, had it occurred in a more severe form, might have caused death.
3. Prolongation of existing hospitalization. Depending on the gestational age, hospitalization for a period of time (at least until the mother’s due date) is expected. If hospitalization is extended beyond this time frame and there is not an alternative medical explanation for this outcome.
4. Persistent or significant incapacity or substantial disruption of the ability to conduct normal life functions.

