### Collection and Recording of Adverse Events

#### Collection Period

Adverse events will be collected from delivery until hospital discharge.

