#### Collecting Adverse Events

Adverse events (including SAEs) may be discovered through any of these methods:

- Interviewing the subject or parent
- Receiving an unsolicited complaint from the subject or parent.
- In addition, an abnormal value or result from a clinical or laboratory evaluation can also indicate an adverse event, as defined in Section 2, *Definitions, Grading and Attribution of Adverse Events*.

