#### Recording Adverse Events

Throughout the study, the investigator will record adverse events and serious adverse events as described previously (Section 2.1, *Definitions*) on the uploadable pdf or printed AE/SAE CRF) regardless of the relationship to study procedure. Once recorded, an

AE/SAE will be followed until it resolves with or without sequelae, or until the end of study participation, or until 30 days after the subject prematurely withdraws (without withdrawing consent)/or is withdrawn from the study, whichever occurs first.

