### **Interim Analysis of Safety Data**

Safety data will be collected throughout the trial. A DSMB will be formed and will review the blinded data at semi-annual intervals. Formal interim statistical analysis will be performed after every third of the participants have completed the trial using the Lan DeMets (at) spending function for between-group comparisons.

The following events will be formally monitored among the maternal/infant dyads:

- Wound infections
- Skin burns
- Hyperthermia at arrival to the warmer - Temperature > 37.5 degrees Celsius
- Length of NICU admission
- Sepsis
- Intraventricular hemorrhage
- Death

Each of these events will be monitored separately.

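### Adverse event collection is given two end points, minutes after birth and hospital discharge, and the form's grade threshold may leave out low-grade burns and wound infections

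*Combined protocol and SAP*

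**What the plan says.** **Collection window.** Under Adverse Event (AE), the plan reasons that study processes occupy only the 2–4 minutes from birth to "arrival to the neonatal resuscitation warmer, adverse events will be collected during this time period". Under Collection Period it says: "Adverse events will be collected from delivery until hospital discharge".

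**Recording rule.** Grading Criteria directs events of grade 3 and above to the AE case report form. Recording Adverse Events sets no grade limit: "Throughout the study, the investigator will record adverse events and serious adverse events as described previously", with a cross-reference to the Definitions section. Medical Monitor Review compiles safety information from those forms, and Planned DSMB Reviews gives the DSMB, as a minimum, a listing of reported events.

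**Monitoring.** Interim Analysis of Safety Data states: "Safety data will be collected throughout the trial". It then says: "The following events will be formally monitored among the maternal/infant dyads". Seven items follow, each monitored separately: wound infections, skin burns, hyperthermia at the warmer, length of NICU stay, sepsis, intraventricular hemorrhage and death.

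**Triggers.** Ad hoc DSMB Reviews and the section on temporary suspension of enrolment each list events that prompt action. The two lists are not worded alike.

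**The concern.** The two windows start together and end at very different times. The short one also does not say whether an event must begin, or be recognised, within it. The cross-reference makes this more than a stray remark: staff who look up what to record are sent to the Definitions section, where the 2–4 minute sentence stands.

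Burns are a direct risk of a heated mattress. Expedited Safety Reporting uses them as its example of an event for which one occurrence can support a causal link. A between-group comparison of burns and wound infections is sound only if both are recorded in the same way, throughout the stay and at every grade. The definition and the form rule each leave room for that not to happen.

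**Working it through.** No stated figure needs reproducing. The check sets the sections side by side, with some counting.

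**1. Which window fits the rest of the safety text?**

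- Serious Adverse Event (SAE) counts a prolonged stay, measured against a hospitalization expected to last at least to the mother's due date: "If hospitalization is extended beyond this time frame and there is not an alternative medical explanation for this outcome". Assume the due date is 40 weeks 0 days (280 days); the documents do not define it. Birth at 36 weeks 6 days is day 258, and 280 − 258 = 22 days. Birth at 32 weeks 0 days is day 224, and 280 − 224 = 56 days. The criterion can be judged only about 22 to 56 days after birth, not within 2–4 minutes.
- Collecting Adverse Events names "Interviewing the subject or parent" and abnormal laboratory results as sources. Neither fits a window of minutes in an operating room.
- Recording Adverse Events and Interim Analysis of Safety Data both speak of the whole study or trial.

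All of these fit Collection Period. The sentence in the definition is the one out of line.

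**2. Which monitored items depend on the AE window?**

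| Item | Recognisable within 2–4 minutes? | Chart Review outcome? |
|---|---|---|
| Wound infections | No | No |
| Skin burns | Depends on when seen | No |
| Hyperthermia at the warmer | Measured as the window closes | Yes |
| Length of NICU stay | No | Yes |
| Sepsis | No | Yes |
| Intraventricular hemorrhage | No | Yes |
| Death | Only if within minutes | Yes |

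Four items would not be recognised in the short window. Three of those four are Chart Review outcomes and are captured there anyway, leaving 4 − 3 = 1, wound infections. Five of the seven are Chart Review outcomes, so 7 − 5 = 2 are not: burns and wound infections.

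For burns, the Protocol section says: "Upon arrival at the warmer, the mattress and wrap will be removed as neonatal evaluation takes place". A mattress burn would begin by about that moment, which is when the short window closes. Read by onset, burns fall inside it and 1 of 7 items is exposed. Read by recognition, a burn first seen after removal falls outside and 2 of 7 are exposed.

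**3. Grade rule.** The plan grades events from 1 to 5. A threshold of grade 3 leaves grades 1 and 2 off the form, 2 of 5 grades. The monitoring list sets no grade for burns or wound infections. Form, compilation and DSMB listing are linked, so what is left off the form may not reach the DSMB.

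**4. Triggers, compared.**

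| | Ad hoc DSMB review | Enrolment halt |
|---|---|---|
| Deaths | Possibly or definitely related | Relatedness not mentioned |
| SAEs, grade 3 and above, in at least 3 people | Unexpected | Related and unexpected |
| Population counted | Those who received the intervention | Study participants |

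The heading of the suspension section links the halt to the ad hoc review. The DSMB also rules on attribution and reviews SAE reports, and SAEs go to the sponsor within 24 hours. This is therefore a conflict of wording and not a gap in oversight.

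**The case against.** The strongest reply is that Collection Period is the titled rule and is clear, while the short window is a remark inside a definition, explained by when study procedures take place. Harm would require staff to prefer that remark to everything else. This limits the likely reach but does not remove the conflict: the remark says when events are collected, not merely when exposure occurs, and the recording instruction points to the section that contains it.

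Second, the infant is examined as the mattress and wrap come off, so most burns might be seen at once. That is fair, and it is why burns are counted as exposed only on the recognition reading.

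Third, Grading Criteria does not expressly exclude grades 1 and 2, Recording Adverse Events read alone would capture them, the DSMB listing is only a minimum, and Chart Review draws on maternal and neonatal records. A grade threshold can also be a reasonable choice in a pilot. All of this stands, so the claim is only that low-grade events could be left off. But neither burns nor wound infections is a listed Chart Review outcome, and the AE form is the only capture route the plan names for them.

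Finally, the burns example in Expedited Safety Reporting concerns serious, unexpected reactions. It shows that the plan regards burns as tied to the procedure; it does not show that low-grade burns are reportable.

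**Conclusion.** The concern holds. The contradiction over the collection window is plain on the page, and nothing in the text available for review says which statement governs. Its reach is narrow: one of the seven monitored items if the short window refers to onset, two if it refers to recognition. The other five are collected as study outcomes whatever the AE window. The form threshold is a second, less certain weakness affecting grades 1 and 2 of the same two events. The trigger lists need consistent wording, or a statement that they are meant to differ.

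The 22 to 56 days rest on the assumed due date and only illustrate the mismatch. The documents give no basis for estimating how many events would be missed. No sample size or power figure is affected. The text should be corrected.

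**What to change.** - In Adverse Event (AE), replace the 2–4 minute collection sentence with the window already given in Collection Period. It would help to state whether discharge means the mother's, the infant's or both, since dyads are monitored.
- In Grading Criteria and the AE form instruction, state that skin burns and wound infections, as monitored in Interim Analysis of Safety Data, are recorded at any grade. The sponsor may also settle the general difference between Grading Criteria and Recording Adverse Events.
- Separately, the sponsor and DSMB should reconcile the ad hoc review and enrolment-halt triggers on relatedness of deaths, relatedness of SAEs and the population counted, or state that the differences are intended. This review does not say which is right.

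The cost is one sentence in the definition, one line in Grading Criteria and the form instruction, and a wording check of the two trigger sections. The downside is a few more low-grade burn and wound infection entries to record.

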##### **Suspected Adverse Reaction (SAR)**

Any adverse event for which there is a reasonable possibility that the investigational procedure caused or contributed to the adverse event. For the purposes of safety reporting, 'reasonable possibility' means there is evidence to suggest a causal relationship between the procedure and the adverse event. A suspected adverse reaction implies a lesser degree of certainty about causality than adverse reaction, which means any adverse event caused by a procedure (21 CFR 312.32(a)).

### Unexpected Adverse Event

An adverse event or suspected adverse reaction may be related to the study agent, or study procedures, or may be unrelated. Procedure-related adverse events or suspected adverse events are considered “unexpected” if not listed in the relevant *package insert* or not listed at the specificity, severity or rate of occurrence that has been observed.

“Unexpected” also refers to adverse events or suspected adverse reactions that are mentioned in the package insert as occurring with a class of drugs or as anticipated from the pharmacological properties of the drug, but are not specifically mentioned as occurring with the particular drug under investigation (21 CFR 312.32(a)).

### Serious Adverse Event (SAE)

An adverse event or suspected adverse reaction is considered “serious” if, in the view of either the investigator or OSCTI, it results in any of the following outcomes (21 CFR 312.32(a)):

1. Death.
2. A life-threatening event: An AE or SAR is considered “life-threatening” if, in the view of either the investigator or OSCTI, its occurrence places the subject at immediate risk of death. It does not include an AE or SAR that, had it occurred in a more severe form, might have caused death.
3. Prolongation of existing hospitalization. Depending on the gestational age, hospitalization for a period of time (at least until the mother’s due date) is expected. If hospitalization is extended beyond this time frame and there is not an alternative medical explanation for this outcome.
4. Persistent or significant incapacity or substantial disruption of the ability to conduct normal life functions.

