#### **Reporting of Serious Adverse Events to OSCTI**

Site investigators will report all serious adverse events (see Section 2.1, *Serious Adverse Event*), regardless of relationship or expectedness within 24 hours of discovering the event. For serious adverse events, all requested information on the AE/SAE uploadable CRF will be provided. However, unavailable details of the event will not delay submission of the known information. As additional details become available, the AE/SAE uploadable CRF will be updated and submitted.

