##### Expedited Safety Reporting

This option applies if the adverse event is classified as one of the following:

**Category 1: Serious and unexpected suspected adverse reaction [SUSAR]** The sponsor shall report any suspected adverse reaction that is both serious and unexpected (see Section 2.1, *Suspected Adverse Reaction* and *Unexpected Adverse Event* and 21 CFR 312.32(c)(1)i). The sponsor shall report an adverse event as a suspected adverse reaction only if there is evidence to suggest a causal relationship between the study drug and the adverse event, such as:

1. A single occurrence of an event that is uncommon and known to be strongly associated with procedure exposure (e.g., burns);
2. One or more occurrences of an event that is not commonly associated with drug exposure, but is otherwise uncommon in the population exposed to the procedure.

3. An aggregate analysis of specific events observed in a clinical trial (such as known consequences of the underlying disease or condition under investigation or other events that commonly occur in the study population independent of the intervention) that indicates those events occur more frequently in the treatment group than in a concurrent or historical control group.

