### Ad hoc DSMB Reviews

In addition to the pre-scheduled data reviews and planned safety monitoring, the DSMB may be called upon for *ad hoc* reviews. The DSMB will review any event that potentially affects safety at their own initiative or at the request of the PIs or OSCTI. In addition, the following events will trigger an *ad hoc* comprehensive DSMB Safety Review:

- Any death that occurs in the study, which is possibly or definitely related to study intervention.
- The occurrence of a Grade 3 or higher unexpected SAE in 3 or more of the study participants who have received the study intervention.

After review of the data, the DSMB will make recommendations regarding study conduct and/or continuation.

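### The SAE definition counts a prolonged stay only past the due date and has no limb for other important events, so some burns and prolonged stays miss the plan's prompt safety reports

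*Combined protocol and SAP*

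**What the plan says.** The section Serious Adverse Event (SAE) makes an event serious, in the view of the investigator or OSCTI, only if it leads to one of four outcomes.

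- **Death.**
- **Immediate risk of death.** This limb is kept narrow: "It does not include an AE or SAR that, had it occurred in a more severe form, might have caused death".
- **Prolonged hospitalization.** Some stay is taken as normal: "hospitalization for a period of time (at least until the mother’s due date) is expected". The qualifying sentence follows: "If hospitalization is extended beyond this time frame and there is not an alternative medical explanation for this outcome". It has no main clause. I read it as the condition under which prolongation counts.
- **Incapacity** that is lasting or significant, or substantially disrupts normal functioning.

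There is no limb for other medically important events.

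Four rules use the definition:

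- **Reporting of Serious Adverse Events to OSCTI:** SAEs are reported "regardless of relationship or expectedness within 24 hours of discovering the event".
- **Expedited Safety Reporting, Category 1:** the reaction must be both serious and unexpected.
- **Ad hoc DSMB Reviews:** one automatic trigger is "The occurrence of a Grade 3 or higher unexpected SAE in 3 or more of the study participants", counted among those who received the intervention.
- **Temporary Suspension of enrollment:** the same count, with relatedness added.

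Interim Analysis of Safety Data names skin burns and length of NICU admission among the events to be monitored, each separately.

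**The concern.** The intervention is an active heat source placed against a preterm infant, so a burn is the obvious device harm, and the plan lists it for monitoring. Yet a burn that needs treatment and lengthens the stay is not serious if it is not immediately life-threatening, causes no significant incapacity and resolves before the due date. The same holds for any prolonged stay that ends before that date, unless another limb applies. Such events do not reach the rules that act within hours or automatically.

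There is a second problem inside the prolongation limb. Asking whether there is another medical explanation is a question of cause. Attribution Definitions makes cause a separate step, with the final determination by the DSMB, and the 24-hour rule applies whatever the relationship. As worded, a site can remove a prolonged stay from SAE reporting before either of those steps is reached. Preterm infants often have a competing reason for a long stay, so the clause could be used often.

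**Working it through.** The plan gives no figure on this point to reproduce. The check is one of logic, with simple arithmetic for size.

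**1. Where the due-date boundary falls.** Inclusion Criteria set gestational age at 32w0d to 36w6d. Taking the due date as 40w0d (280 days), days from birth to due date = 280 − gestational age in days.

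| Birth at | Days of gestation | Days to due date |
|---|---|---|
| 32w0d | 224 | 56 |
| 34w6d | 244 | 36 |
| 35w0d | 245 | 35 |
| 36w6d | 258 | 22 |

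**2. How much prolongation can go uncounted.** With E the stay the infant would have had without the event, the most that can go uncounted is (280 − gestational age) − E. The documents do not give E. As an assumption, E at half the interval leaves 28 days at 32w0d and 11 days at 36w6d. Only E = 0 gives the full 56 and 22. The Protocol section lets infants go to the mother-baby or post-anesthesia unit, and NICU admission is an outcome, so the trial does not itself assume that every infant stays to the due date.

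**3. A Grade 3 burn against the four outcomes.** Grading Criteria define Grade 3 as severe, Grade 4 as life-threatening or disabling, and Grade 5 as death. A Grade 3 burn is thus below the first two limbs and can be an SAE only through prolongation or incapacity. If it resolves before the due date without significant incapacity, neither applies. Three such infants would not produce the automatic review or the halt.

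**4. Illustration of the three-participant trigger.** With 74 enrolled 1:1, about 37 are treated. Let p be the chance that a treated infant has a Grade 3 or higher unexpected event and s the share of those events that meet one of the four outcomes. Then P(3 or more) = 1 − Σ C(37,k) q^k (1−q)^(37−k) for k = 0 to 2, with q = p × s. Both p and s are assumptions; the documents give neither.

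| p | s = 1 | s = 0.5 | s = 0.25 |
|---|---|---|---|
| 1% | 0.6% | 0.09% | 0.01% |
| 2% | 3.8% | 0.6% | 0.09% |
| 5% | 28% | 6.5% | 1.1% |
| 10% | 73% | 28% | 6.5% |

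With s = 0 the probability is zero at every p.

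**5. Speed of the other routes.** Statistical Methods expects 74 patients in about 11 months, or 74/11 ≈ 6.7 a month. A semiannual review would come after about 6 × 6.7 ≈ 40 enrolled, roughly 20 of them treated. The formal safety analysis comes after each third, 74/3 ≈ 25 participants. The 24-hour notice to the DSMB in Planned DSMB Reviews covers Expedited Safety Reports only.

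**The case against.** The strongest reply is that the harms are not unwatched, and that is correct. The DSMB receives a listing of all reported AEs. Skin burns and NICU stay have their own interim comparisons. The DSMB may review any event bearing on safety, on its own initiative or on request. Category 2 reporting has no seriousness condition, and Study Stopping Rules cover severe as well as serious events. What remains is a gap in prompt and automatic action.

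Four stronger readings are tempting, and the documents do not support them.

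- **That the plan itself calls a single burn serious and so contradicts its own definition.** The Category 1 wording, "A single occurrence of an event that is uncommon and known to be strongly associated with procedure exposure (e.g., burns", illustrates evidence of causation. Seriousness is a separate condition in the same section.
- **That burns are left out of the definition.** The list is by outcome, not diagnosis. A burn leading to any of the four outcomes is an SAE.
- **That 3 to 8 weeks of prolongation would go uncounted.** The 22 to 56 days are a ceiling from which the expected stay must be subtracted.
- **That wider seriousness wording would by itself restore every trigger.** Category 1, the ad hoc trigger and the halt also require the event to be unexpected, which Unexpected Adverse Event ties to a package insert that is not in the documents. The ad hoc trigger and the halt also require Grade 3 or higher, and the halt requires relatedness.

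It is also fair to say that the alternative-explanation clause would not block a clear device burn, since the burn would itself be the explanation. The clause matters where the cause is open.

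**Conclusion.** The point holds in a limited form. A burn or prolonged stay below the four outcomes is not an SAE, and so misses the 24-hour report, the Category 1 report and the automatic three-participant review and halt. The triggers on death are unaffected. For prolongation the boundary lies 22 to 56 days after birth, less the expected stay. Placing a test of cause inside seriousness also conflicts with Attribution Definitions and with the 24-hour rule.

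This rests on a due date of 40w0d, on reading the incomplete sentence in the prolongation limb as a condition, and on treating the four outcomes as a closed list. I make no claim about whether the list matches the regulation it cites, whose text is not in the documents.

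**What to change.** Reconcile the Serious Adverse Event section with Attribution Definitions, the 24-hour reporting rule, Expedited Safety Reporting, the two DSMB trigger sections and Interim Analysis of Safety Data:

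- **(a)** Delete the alternative-explanation condition, so that seriousness is judged first and attribution separately.
- **(b)** Judge prolongation against the stay expected for that infant without the event, not against the due date.
- **(c)** State that skin burns of Grade 3 or higher, regardless of attribution, are handled as SAEs: reportable within 24 hours and counted toward the ad hoc review and enrollment halt, subject to the other conditions of those rules. The grade threshold keeps trivial redness out.

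The cost is protocol wording, a few more SAE forms, and some judgment about expected stay in a trial where the clinical teams are not blinded. Recording the expected stay and its basis on the form would make that judgment open to review. The plan should also say whether burns count as expected under the package insert, because Category 1 and both three-participant triggers still turn on that.
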